First date when all symptom resolution status is changed to 'Yes' - first dosing date + 1.

If a patient has not experienced symptom resolution by completion or early discontinuation of study/study treatment, the patient will be censored at the date of their last visit during the post-treatment period.

Time to all symptom resolution will be applying the same KM methods and Cox proportional hazard models introduced in the time to hospitalization section.

Symptom Improvement

Symptom improvement is defined as a change in severity of overall symptoms * from a higher score to a lower score, which is defined as following:

symptoms scored as moderate or severe at baseline are scored as mild or absent,
OR

symptoms scored as mild or absent at baseline are scored as absent.

Note: * The overall symptoms question (overall question 1) under overall COVID-19 related symptoms from COVID-19-Related Symptom Questionnaire is included here.

Additionally, symptom improvement will be defined by individual symptom questions from symptom questionnaire as below and related outputs will be noted as sensitivity analysis. It is defined as a patient experiencing both:

symptoms * scored as moderate or severe at baseline are subsequently scored as mild or absent,

AND

symptoms * scored as mild or absent at baseline are subsequently scored as absent.

Note: * Seven individual questions from COVID-19-Related Symptom Questionnaire are included here: questions 3, 4, 5, 6, 7, 8 and 9.

The proportion of subjects with symptom improvement at Days 3, 7, 11, 14 and 28 will be summarized by treatment in frequency tables and listed using mITT set. Generalized estimating equation (GEE) model is fitted with the response of symptom improvement mapped to categories of Yes or No and with treatment, age, stratification factors (sex, race and ethnicity, and number of risk factors), time effect and time*treatment interaction terms included in the model as covariates. Odds ratios with 95% confidence intervals and p-values will be present.

Time to Symptom Improvement

Time to symptom improvement (in days) is defined as:

Date when symptom improvement status is changed to 'Yes' - first dosing date + 1.

If a patient has not experienced symptom improvement by completion or early discontinuation of study/study treatment, the patient will be censored at the date of their last visit during the post-treatment period.

Time to symptom improvement will be applying the same KM methods and Cox proportional hazard models introduced in the time to hospitalization section.

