		
 ○ With age ≥ 50 years and days from symptom onset to study randomization ≤ 5 days and/or days from the positive SARS-CoV-2 prior to first dosing ≤ 3 days With age ≥ 50 years and higher than normal biomarkers (CRP, Ferritin, D-dimer) • Regarding statistical analysis of viral load, more analyses were added, including two sample t-tests between treatment groups at Days 3, 7, 14, and 28; ANCOVA analysis of change in viral load from baseline at days 3 and 28; and MMRM modeling of change in viral load at day 3, 7, 14, and 28 from baseline. • Added sustained 100% viral reduction and associated statistical analyses of GEE, KM plots, log rank test and Cox regression models. • Added subgroup analysis of primary endpoints based on (1) Days from the Positive SARS-CoV-2 Prior to First Dosing; (2) Biomarker status at baseline; and (3) Common types of viral variants. • More details were added to the time-to-event analysis. • Updated statistical model for viral resistance. • Removed the following analyses 
 ○ Proportion of subjects admitted to an intensive care unit (ICU) due to COVID-19 by Day 28 ○ Days in ICU due to all causes or COVID-19 by Day 28 ○ Time to ICU by Day 28 ○ Proportion of subjects requiring invasive mechanical ventilation or ECMO due to COVID-19 by Day 28 ○ Days on supplemental oxygen/high flow oxygen devices/ invasive mechanical ventilation due to COVID-19 by Day 28 ○ Proportion of subjects with all-cause mortality by Day 28 and Day 42 ○ Proportion of subjects with COVID-19 related mortality by Day 28 and Day 42 • Corrected “RT-PCR” as “ddPCR”. • Removed subgroup analysis of primary endpoint based on Concomitant medication of interest used. • Section 4.10.1.1.3 was added to justify the change in the SAP from the protocol.
2.0	14 Mar 2022	Finalized

LIST OF ABBREVIATIONS

Abbreviation / Acronym	Definition / Expansion
AACR	American Association for Cancer Research
ACE2	Angiotensin Converting Enzyme 2
ACVPU	Alert, Consciousness, Verbal, Pain, Unresponsive Scale
AE	Adverse Event
ALT	Alanine Transaminase
ANC	Absolute Neutrophil Count
aPTT	Activated Partial Thromboplastin Time
AR	Androgen Receptor
ARDS	Acute Respiratory Distress Syndrome
AST	Aspartate Transaminase
ATC	Anatomical Therapeutic Chemical
AUC	Area under the Curve
BID	Twice a Day
BP	Blood Pressure
BMI	Body Mass Index
CDC	Centers for Disease Control and Prevention
CFR	Code of Federal Regulations
CHO	Chinese Hamster Ovary

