4.10.3 Secondary Efficacy Variables

Hospitalization Percentage

Hospitalization percentage is defined as the percentage of subjects who experience any of the following events due to all causes by Day 28:

- Hospitalization for \geq 24 hours or
- Supplemental oxygen for \geq 24 hours in response to $\text{SpO}_2 \leq 93\%$ or
- Death

The same process used for the primary endpoint analysis will be used to compare the difference between treatment groups.

The following sensitivity analysis for hospitalization percentage will be performed among subset of mITT subjects:

- With dosing days > 7 days;
- With one or several major risk factors below:
 - Single risk factor: age (≥ 50 years; ≥ 60 years), major underlying medical conditions (overweight, obesity, hypertension, diabetes, smoking);
 - Combination of age factor in column 1 and other major underlying medical conditions in column 2 in the table below (e.g., age ≥ 50 years and/or obesity at randomization; age ≥ 60 years and/or obesity at randomization);

Age	Major underlying medical conditions
≥ 50 years	Overweight
≥ 60 years	Obesity Hypertension Diabetes Smoking

- With aged ≥ 50 years and days from symptom onset to study randomization ≤ 5 days and days from the positive SARS-CoV-2 Prior to first dosing ≤ 3 days;
- With aged ≥ 50 years and higher than normal biomarkers (CRP, Ferritin, D-dimer).

All sensitivity analyses will be conducted using one-sided CMH chi-square tests used for the primary endpoint analysis. Forest plots for the sensitivity analysis will be presented.

Change from Baseline to Days 3, 7, 14 and 28 in SARS CoV-2 Viral Load

Change of SARS-CoV-2 viral load from baseline, which will be evaluated in log base 10 scale, will be summarized, and plotted by treatment group and listed. Two sample t-tests will be used to compare differences in the change of SARS-CoV-2 viral load between treatment groups at Day 3, 7, 14 and 28, respectively.

Also, an analysis of covariance (ANCOVA) model will be used to compare the change from baseline in SARS-CoV-2 viral load at Day 3 with fixed effects for treatment group, age and stratification factors (sex, race and ethnicity, and number of risk factors), and baseline viral load as a covariate. If systematic pattern is identified from the residual of predicted values, a transformation of the baseline viral load will be employed to improve the performance of the model. Estimated treatment differences

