in comparison to placebo along with corresponding two-sided 95% confidence intervals (CIs) and p-values will also be presented.

Additionally, change from baseline in SARS-CoV-2 viral load at Day 3, 7, 14 and 28 will be compared using a mixed model repeated measures (MMRM). The model will include treatment group, visit, treatment-by-visit interaction, age and stratification factors (sex, race and ethnicity, and number of risk factors) as fixed effects, baseline viral load as a covariate, and subject as a random effect. If the unstructured covariance matrix fails to converge, the heterogeneous Toeplitz covariance structure, followed by the heterogeneous autoregressive covariance structure, will be used. If systematic pattern is found in the residual of predicted values, a transformation of the baseline viral load will be employed to improve the performance of the model. Comparisons of GT0918 to placebo for change from baseline in viral load and the corresponding two-sided 95% CIs along with p-values will be calculated and plotted based on the MMRM model at each visit.

Sustained 100% SARS CoV-2 Viral Reduction

SARS-CoV-2 viral reduction (%) is calculated as

$$(\text{viral load after baseline} - \text{viral load at baseline}) / (\text{viral load at baseline}) * 100\%.$$

If the value of SARS-CoV-2 viral reduction is greater than or equal to 100 the result of 100% SARS CoV-2 viral reduction will be set as "Yes". Otherwise, a negative result of "No" will be obtained.

Sustained 100% SARS CoV-2 viral reduction (Yes/No) is defined when at least two consecutive negative ("No") tests (≥ 24 hours apart) are obtained. The date of sustained 100% SARS CoV-2 viral reduction is defined as the earlier date of the consecutive negative tests.

The proportion of subjects that achieve sustained 100% SARS CoV-2 viral reduction at Days 3, 7, 14, and 28 will be summarized by treatment in frequency tables, plotted and listed. Generalized estimating equation (GEE) model will be used to model the proportions of achieving SARS-CoV-2 clearance at different visits. The model will consider treatment group, visit, treatment-by-visit interaction, age and stratification factors (sex, race and ethnicity, and number of risk factors) as fixed effects, and subject as a random effect. Comparisons of GT0918 to placebo for odds ratios (ORs), corresponding 95% CIs and p-values will be calculated at each visit.

Time to Sustained 100% SARS CoV-2 Viral Reduction

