Time to sustained 100% SARS-CoV-2 viral reduction (in days) is defined as:

Date when sustained 100% SARS CoV-2 viral reduction is changed to 'Yes' - first dosing date + 1.

If a patient has not experienced SARS-CoV-2 clearance by completion or early discontinuation of study/study treatment, the patient will be censored at the date of their last visit during the post-treatment period.

Time to sustained 100% SARS CoV-2 viral reduction and will be summarized and plotted by treatment group with mITT set using the Kaplan-Meier (KM) method. The 2-sided 95% CIs for the 25th, 50th and 75th percentiles, as well as at days 3, 7, 14 and 28 using the Brookmeyer and Crowley method will be reported when estimable. P-value will be obtained from the log-rank test stratified by age, and sex, race and ethnicity, and number of risk factors at randomization. Hazard ratios and corresponding 95% confidence intervals will be obtained from a Cox proportional hazard model which treated treatment group as a unique covariate, and age, and sex, race and ethnicity, and number

of risk factors as stratas. The Cox proportional hazard model will be also performed by subgroup of duration since symptom onset to randomization category (≤ 3 days; > 3 days).

SARS CoV-2 Viral Clearance

SARS-CoV-2 Viral clearance (Yes/No) is defined when at least two consecutive negative tests proceed a positive test with all tests ≥ 24 hours apart. The date of viral clearance is defined as the earliest date between the consecutive negative tests.

The proportion of subjects that achieve SARS-CoV-2 clearance at Days 3, 7, 14, and 28 will be summarized by treatment in frequency tables, plotted and listed. Viral clearance can only be achieved (Yes) at days with a negative result. Generalized estimating equation (GEE) model will be used to model the proportions of achieving SARS-CoV-2 clearance at different visits. The model will consider treatment group, visit, treatment-by-visit interaction, age and stratification factors (sex, race and ethnicity, and number of risk factors) as fixed effects, and subject as a random effect. Comparisons of GT0918 to placebo for odds ratios (ORs), corresponding 95% CIs and p-values will be calculated at each visit.

Time to SARS-CoV-2 Clearance

Time to SARS-CoV-2 clearance (in days) is defined as:

Date when SARS-CoV-2 clearance status is changed to 'Yes' - first dosing date + 1.

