If a patient has not experienced SARS-CoV-2 clearance by completion or early discontinuation of study/study treatment, the patient will be censored at the date of their last visit during the post-treatment period.

Time to SARS-CoV-2 clearance will be applying the same KM methods and Cox proportional hazard models introduced for the time to sustained 100% SARS CoV-2 viral reduction analysis.

Viral Load AUC

SARS-CoV-2 viral load area under the concentration-time curve (AUC) will be calculated according to the linear trapezoidal rule using the measured SARS-CoV-2 viral load-time values above the lower limit of quantification (LoQ) at Days 3, 7, 14 and 28. Per ICON central lab, LoQ is 59.9 copies/mL. No imputations of missing data will be conducted. No AUC(0-D28) values will be calculated when Day 1 pre-dose and/or Day 28 values are missing, or if there are more than 3 values missing in the profile. The AUC (0-D28) will be summarized and plotted by treatment group and listed.

Viral Resistance by Day 28

The proportion of viral resistance at day 28 will be summarized by treatment group and listed. The CMH chi-square test introduced for the primary endpoint analysis will be used to compare the difference of proportion of viral resistance between treatment groups by day 28.

Viral resistance is defined as when subjects:

- Are not able to show two consecutive negative test results via ddPCR testing by Day 28 without any missing scheduled tests, and/or

- Show a positive real-time ddPCR test result after two consecutive negative ddPCR test results, and/or
- A confirmed rise in SARS-CoV-2 RNA of ≥ 1 log10 after achieving nadir on treatment.

COVID-19 Ordinal Outcomes Scale

Below summaries will be provided using mITT set:

- The percentage of subjects at each clinical status using NIAID 8-point ordinal scale at Days 3, 7, 14, and 28

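### As printed, the SAP's sustained 100% viral reduction endpoint counts subjects whose virus is unchanged or has risen less than twofold

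*SAP*

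**What the plan says.** The endpoint is not in the protocol (sections 3 and 7.2.7). The SAP revision history records its arrival: "Added sustained 100% viral reduction and associated statistical analyses of GEE". SAP 3.3.2 lists it as a secondary endpoint twice, as proportions at Days 3, 7, 14 and 28 and as a time to event.

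The subsection on sustained 100% viral reduction in SAP 4.10.3 sets these rules:

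- Percentage reduction is (load after baseline minus load at baseline) divided by load at baseline, times 100.
- "If the value of SARS-CoV-2 viral reduction is greater than or equal to 100", the test is a Yes. Every other value is a No, which the text also calls negative.
- "Sustained 100% SARS CoV-2 viral reduction (Yes/No) is defined when at least two consecutive negative" tests, at least 24 hours apart, are obtained. The SAP spells out in brackets that negative here means No. The event takes the earlier of the two dates.

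Three neighbouring subsections bear on the reading:

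- Viral clearance uses the same two-test structure, "at least two consecutive negative tests proceed a positive test", but there negative has its usual virological meaning.
- Viral resistance includes subjects who "Are not able to show two consecutive negative test results via ddPCR testing by Day 28" with no scheduled test missing.
- The change-from-baseline analysis names its scale: "Change of SARS-CoV-2 viral load from baseline, which will be evaluated in log base 10 scale". The reduction formula names none.

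**The concern.** The sign of the formula and the cut-off contradict each other: a true reduction can never reach +100, and only growth can. The sustained rule then selects the No results. The two errors do not cancel. Together they admit subjects who cleared the virus along with almost everyone who did not.

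The flag feeds frequency tables, GEE odds ratios, Kaplan-Meier curves, the stratified log-rank test and Cox models. If it is programmed as printed, responders and non-responders get the same event, often on the same day, and the endpoint loses its ability to show a treatment difference. SAP 4.1 requires outputs to be checked independently, but a checker working from this text would either reproduce the error or disagree with the programmer, with nothing in the SAP to settle it.

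**Working it through.** The SAP gives no numerical result to reproduce here, so the check applies the printed rule to example subjects.

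**Inputs.** The formula, cut-off, two-test rule and dating rule come from SAP 4.10.3. Swab days 3, 7, 14 and 28 come from the schedule of activities. The limit of quantification (LoQ), 59.9 copies/mL, comes from the Viral Load AUC text in SAP 4.10.3. A baseline of 10^6 copies/mL is assumed for illustration. On the copies/mL scale the classification depends only on the ratio of follow-up to baseline.

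**Step 1: one test.** R = (V_t - V_0)/V_0 × 100 = (V_t/V_0 - 1) × 100. So R ≥ 100 exactly when V_t/V_0 ≥ 2, and R cannot go below -100.

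| Follow-up load (copies/mL) | R | Printed flag | Two in a row count as sustained? |
|---|---|---|---|
| 0 | -100 | No | yes |
| 5 × 10^5 (halved) | -50 | No | yes |
| 10^6 (unchanged) | 0 | No | yes |
| 1.9 × 10^6 | +90 | No | yes |
| 2 × 10^6 (doubled) | +100 | Yes | no |

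**Step 2: event dates.** Each cell is the day of the first of two consecutive qualifying swabs.

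| Loads at Days 3, 7, 14, 28 | As printed | Sign corrected only | Yes/No corrected only | Both corrected |
|---|---|---|---|---|
| 0, 0, 0, 0 | 3 | none | none | 3 |
| 10^4, 0, 0, 0 | 3 | none | none | 7 |
| 10^5, 10^3, 0, 0 | 3 | 3 | none | 14 |
| 10^6 at all four | 3 | 3 | none | none |
| 5 × 10^5 at all four | 3 | 3 | none | none |
| 1.9 × 10^6 twice, then 10^6 twice | 3 | 3 | none | none |
| 2 × 10^6 twice, then 0 twice | 14 | 3 | 3 | 14 |

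As printed, the second and third subjects are dated 7 - 3 = 4 and 14 - 3 = 11 days early. The next three receive an event they should not have. The last row shows the exception: a subject at or above twice baseline on Days 3 and 7 is not given a Day 3 event. Correcting one reversal alone does not help. With only the sign corrected, subjects at zero from Day 3 or Day 7 are lost. With only the Yes/No rule corrected, only subjects with two consecutive tests at or above twice baseline count.

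**Step 3: clash with another definition.** The subject with 10^6 at all four swabs has no two consecutive negative ddPCR results by Day 28 and no missing swab. That subject is viral resistance under one subsection and sustained 100% reduction under another.

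**Step 4: scale.** On log10, a baseline of 6 would need a follow-up of 12 (10^12 copies/mL) for a Yes. A doubling gives (6.301 - 6)/6 × 100 = 5.02, so even a doubling would count as sustained reduction.

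**Step 5: LoQ after correction.** With R' = (V_0 - V_t)/V_0 × 100:

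| Baseline | Below-LoQ result entered as 59.9 | as 29.95 (half the LoQ) | as 0 |
|---|---|---|---|
| 10^3 | 94.01 | 97.005 | 100 |
| 10^6 | 99.994 | 99.997 | 100 |

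Only entry as zero reaches 100, and SAP 4.10.3 does not say which value is used.

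**The case against.** The strongest reply is that the intent is plain. The endpoint's name, the phrase about consecutive negatives and the GEE sentence ("model the proportions of achieving SARS-CoV-2 clearance at different visits") all point to two consecutive tests with no virus. So does the censoring sentence ("If a patient has not experienced SARS-CoV-2 clearance by completion or early discontinuation"). A competent programmer might read it that way, and nothing in the documents shows that the printed rule was coded. The reach is also limited: clearance is defined separately and analysed with the same methods, and so is change from baseline. The twofold boundary holds only in copies/mL, a scale the subsection does not state.

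The limits on reach stand. This is very probably a drafting slip. The primary endpoint, the clearance endpoint and the change-from-baseline analyses are untouched. The only multiplicity adjustment (SAP 4.10.1.2) concerns the interim analysis, so no formal claim depends on this endpoint. The scale point also stands, but a log10 reading makes the rule looser, not sounder. The appeal to intent does not rescue the text: the SAP itself equates negative with No, no other section corrects it, and an obvious-looking repair of one reversal yields another wrong endpoint.

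**Conclusion.** The concern holds. Read literally, sustained 100% viral reduction means two consecutive results below twice baseline, at least 24 hours apart, and it is met by subjects with unchanged virus, a partial fall or a rise of less than twofold. In the examples, true responders are dated 0, 4 or 11 days early, and subjects who never clear are given an event at Day 3.

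The exact twofold boundary assumes copies/mL. The dates assume swabs on the nominal days and an illustrative baseline of 10^6. The effect on results assumes the rule is programmed as printed. This should be corrected because it spoils a listed secondary endpoint, but it does not threaten the trial's primary conclusion.

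**What to change.** Two changes follow directly from the text and must be made together:

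1. Define reduction (%) as (baseline - follow-up)/baseline × 100, on the copies/mL scale, with Yes when it equals 100.
2. Define sustained as two consecutive Yes results at least 24 hours apart, dated at the first.

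The remaining points are specification choices to settle before unblinding:

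- State how results below 59.9 copies/mL enter the formula. One option sets all of them to zero and labels the endpoint as below LoQ, which counts detectable but unquantifiable virus as full reduction. The other sets only target-not-detected results to zero, which requires the laboratory to report them separately.
- State that a subject whose baseline is zero under that rule has no defined percentage. Say how such subjects are handled (for example, as not evaluable) and report their number per arm. Excluding them can make the denominator smaller than the mITT set; the documents do not give their number.
- Make the GEE and censoring sentences name this endpoint instead of clearance.

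The cost is a documented SAP amendment and a change to the derivation code. No new data are needed.

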### 1.2.3.2 Clinical Study in COVID-19

A randomized, double-blinded, clinical study of GT0918 was done in Brazil for both male and female subjects with mild or moderate COVID-19 illness (NCT04446429). Two hundred and sixty-two (262) men were included in the study. 134 men were assigned to the GT0918 group and 128 men were assigned to the control group. The mean age was 44.5±7.7 years old. Thirty-five subjects (27%) were hospitalized in the control group compared to 0 patients in the GT0918 group by Day 30. The proportion of COVID-19 subjects hospitalized was significantly different between the GT0918 and control arms;  $p<0.0001$ . No subject receiving GT0918 died compared to 2% in the control group. Additionally, it also showed a clinical meaningful SARS-CoV-2 viral load reduction and clearance in the GT0918 group compared to the placebo group (RT-PCR positive rate: 42.5% vs 93.8% on Day 7, 15.0% vs 56.2% on Day 14 and 10.0% vs 43.8% on Day 28, respectively).

Treatment-emergent adverse events were reported for 34% of subjects in the GT0918 group and for 61% of subjects in the placebo group. SAEs were only reported in the placebo group. There was no AE leading to discontinuation.

The most frequently reported TEAEs (occurring in  $\geq 10\%$  of subjects) were diarrhea (21%), dehydration (15%), nausea (14%), abdominal pain (12%), dyspepsia (11%) and back pain (10%) in the GT0918 group. The most frequently reported TEAE were disease progression (54%), fatigue (45%), shortness of breath (36%), fever (20%), dehydration (14%), anosmia (13%), ageusia (12%), back pain (12%), and ear pain (10%) in the placebo group. Gastrointestinal TEAE were more frequent in the GT0918 group. General, respiratory, and nerve system TEAEs are more frequent in the placebo group. The TEAEs suspected to be related with study treatment ( $\geq 10\%$ ) were diarrhea, nausea, abdominal pain and dyspepsia in the GT0918 group. No SAE was reported in the GT0918 group. Acute respiratory distress syndrome was reported as SAE in 27% of the subjects in the placebo group.

178 female subjects were randomized to the study with 76 in the GT0918 group and 102 in the control group. All subjects were also treated with the standard of care.

The mean age was 44.2 years old. Nineteen subjects (19%) were hospitalized in the control group compared to 2 patients (3%) in the GT0918 group by Day 30. ( $p<0.0001$ ). No subject receiving GT0918 died compared to one (1%) in the control group.

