### 7.1.2 Treatment Period

All subjects who are randomized to the study are considered as entering the treatment period. The subjects will be treated 14 consecutive days or less due to AE, lost to follow-up or consent withdrawal. During the treatment period, subjects will self-administrated GT0918 or matched placebo orally around 30 minutes after a meal, the dose should be given the same time each day (+/- 2 hours for medication scheduling). Subjects also need to record the time/date of dose with provided Subject Diary daily as well as completion of the questionnaire which allows subjects to self-evaluate their COVID-19 symptoms. Any dose that is delayed may be given later that calendar day. Any dose that is missed (not given that calendar day) is not made up, which should

---

be documented as dose missing on Subject Diary with a reason. The treatment course continues as described above even if the subject becomes SARS-COV-2 test negative.

On Days 3, 7, 14 and 28, nasopharyngeal swabs will be collected for viral load tests, meantime vital sign or other assessments will be performed and PK samples collection will be done per [Schedule of Activities \(SoA\)](#). On Day 14, safety laboratory tests are needed to evaluate clinical outcome and ensure safety. The above visits are preferred subjects in person to sites. However, infection control or other restrictions may limit the ability of the subject to return to sites. In this case, the visits may be conducted as outpatient clinic or home visits. The planned visit schedules and visit types/location should be discussed and confirmed during screening visit with every subject, any future changes will be coordinated according in advance.

Hospitalization should be closely monitored and documented with subject's source and eCRF as described in [Section 7.2.1.1](#).

Meantime, the subjects' clinical status as detailed in [Section 7.2.1.2](#) will be recorded in the eCRF.

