Subject Diary should be completed every day since screening visit until D14 or the last dose.

Questionnaire should be completed every day since screening visit to the end of post-treatment. For details refer to Section 7.2.6.

12. Chest X-ray or CT-Scan or 12-ECG can be done per investigator's discretion. If investigator deems the result is clinically significant, the result should be recorded with eCRF.

13. Hospitalization events: if the subject is hospitalized, the treatment may be continued to the 14 days per PI. Hospitalization is defined as ≥ 24 hours in hospital of care. For details refer to Section 7.1.2.

Record if the following events occur:

- Emergency room visits
- Hospitalized
- ICU admittance
- Extended care facility admittance
- Discharge

14. Documentation from hospital records is acceptable.

Includes:

- Limitation on activities due to COVID-19
- Ongoing hospital medical care
- Supplemental oxygen
- Non-invasive ventilation or high flow oxygen device
- Mechanical ventilation
- ECMO, or

15. Adverse events: any events that occur after signing the informed consent are considered AEs as defined in Section 10.3.

16. Concomitant medications: all medications administered within 30 days prior to the first dose of study treatment through 30 days after the last dose of study treatment will be recorded in the concomitant medications, for details refer to Section 6.4.

17. Pharmacokinetics (PK) samples only need to be taken for at least 200 subjects, who will be assigned according. For details refer to Section 7.2.3.

18. All women regardless of childbearing potential must complete a serum pregnancy test at screening visit, urinary pregnancy test on day 28 as per the schedule of assessment for women of childbearing potential. Local laboratories will be used for the analysis of serum and urinary pregnancy tests.

19. Early withdrawal (EW): if the subject is early withdrawn from this study for any reason (Section 7.1.4), the subject should complete the EW visit, and the visit should occur within 2 days of the EW day. The subject will go to the safety follow-up period for additional 28 days after his last dose.

20. D42 (or 28 days ± 2 post last dose if subject is withdrawn early) safety follow-up visit is phone call visit.

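### Viral clearance needs two consecutive negative swabs but the last scheduled swab is Day 28, so the Day 28 result is not the proportion cleared by Day 28

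*SAP*

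**What the plan says.** SAP 4.10.3 gives three rules for clearance:

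- It "is defined when at least two consecutive negative tests proceed a positive test with all tests ≥ 24 hours apart". I read "proceed" (the SAP's word) as follow.
- "The date of viral clearance is defined as the earliest date between the consecutive negative tests".
- "Viral clearance can only be achieved (Yes) at days with a negative result".

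The results are then tabulated by visit: "The proportion of subjects that achieve SARS-CoV-2 clearance at Days 3, 7, 14, and 28 will be summarized by treatment". A GEE model gives an odds ratio at each visit. Time to clearance uses Kaplan-Meier estimates, including one at Day 28, with a log-rank test and Cox model. For a subject without clearance, "the patient will be censored at the date of their last visit during the post-treatment period".

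On sampling, Protocol 7.1.2 states: "On Days 3, 7, 14 and 28, nasopharyngeal swabs will be collected for viral load tests". The schedule of activities adds swabs at screening and at early withdrawal. The only later contact is Day 42, where, according to SAP Appendix 6.1 note 20, the "safety follow-up visit is phone call visit".

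Protocol 10.5.2.7 and 10.5.2.8 ask for the proportion cleared at Day 28 and for time to clearance evaluated to Day 28. Neither imposes a two-negative rule. The SAP adds the rule but does not say how an unconfirmed negative at the final swab is handled.

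**The concern.** A rule that needs a second negative cannot be met by a first negative at the final swab. A subject positive at Day 14 and negative at Day 28, with no earlier confirmed pair, is recorded as a failure at Day 28 because the schedule ends, not because of anything observed. The Day 28 row then describes clearance that began by Day 14, under a label that reads as clearance by Day 28.

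This matters for interpretation. Suppose treatment only speeds clearance and placebo catches up by Day 28. The confirmed-clearance table would still carry the Day 14 gap into the Day 28 row, and it could be read as a lasting difference. Viral clearance at Day 28 and time to clearance are listed secondary endpoints.

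**Working it through.** The plan states no figure that bears on this point, so there is none to reproduce. The check has two parts.

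**1. Applying the rule to every swab pattern.** Take baseline as positive and write N (negative) or P (positive) for Days 3, 7, 14 and 28 in order. There are 2^4 = 16 complete patterns. Require two consecutive negatives, date clearance to the first, and score Yes at a visit only if its own swab is negative.

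| Result | Patterns |
|---|---|
| Clearance dated to Day 28 | none |
| Yes at both Day 14 and Day 28 | NNNN, NPNN, PNNN, PPNN |
| Yes at Day 28 only | NNPN (return to positive, then negative) |
| Yes at Day 14 only | NNNP, PNNP (return to positive) |
| Swab-negative at Day 28 but scored No | PPPN, NPPN, PNPN |

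If no subject returns to positive, only NNNN, PNNN, PPNN, PPPN and PPPP remain. Day 14 Yes and Day 28 Yes are then the same three patterns, and PPPN is the one lost.

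Now allow missing swabs (3^4 = 81 patterns), taking "consecutive" to mean consecutive among available swabs, which the SAP does not specify. Besides NNPN, Day 28 gains only subjects with a missing Day 14 swab and an earlier negative, such as PNM-N (M = missing). No subject first negative at Day 28 is ever scored cleared. Dating clearance to the second negative would let NPNN and PPNN enter at Day 28, but PPPN would still be a failure.

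For time to clearance, the last scheduled day on which an event can be dated is therefore the Day 14 visit. Only an unscheduled or early-withdrawal swab could create a later event.

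**2. Illustrating the size.** The inputs are the RT-PCR positivity rates in Protocol 1.2.3.2, GT0918 vs control: "15.0% vs 56.2% on Day 14 and 10.0% vs 43.8% on Day 28". They appear in the account of the male cohort of the earlier trial. Assume no return to positive.

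- Swab-negative at Day 28 = 1 − Day 28 positivity: 1 − 0.100 = 90.0% and 1 − 0.438 = 56.2%. The difference is 33.8 points.
- SAP rule at Day 28 = negative at both Day 14 and Day 28 = 1 − Day 14 positivity: 1 − 0.150 = 85.0% and 1 − 0.562 = 43.8%. The difference is 41.2 points, identical to Day 14.
- First negative between Days 14 and 28: 0.150 − 0.100 = 5.0% and 0.562 − 0.438 = 12.4%. With 334 subjects per arm (668/2) this is about 17 and 41 subjects. As shares of the Day 28 negatives, they are 5.0/90.0 = 5.6% and 12.4/56.2 = 22.1%.
- Excess in the risk difference: 41.2 − 33.8 = 7.4 points.
- Odds ratio, single swab: (0.900/0.100)/(0.562/0.438) = 7.01.
- Odds ratio, SAP rule: (0.850/0.150)/(0.438/0.562) = 7.27, about 4% higher.

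A purely hypothetical catch-up case shows that the odds ratio is not always so little affected. If both arms were 90.0% negative at Day 28 with the same Day 14 rates, the single-swab odds ratio would be 1, while the SAP rule would still give 7.27.

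**The case against.** A good deal of the opposing case stands.

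- **Effect scale.** The SAP compares arms by odds ratio. In the illustration the odds ratio moves only from 7.01 to 7.27, so the distortion there is mainly in the tabulated proportions.
- **One weak scenario.** The rates come from men and from RT-PCR. This trial enrols both sexes, and its SAP specifies ddPCR. If nearly everyone clears by Day 14, the effect is close to nil.
- **Rebound.** The SAP's viral resistance definition anticipates a positive after two negatives. Such subjects change status between Days 14 and 28, so the Day 28 row does carry information on durability.
- **Other analyses.** The t-tests and the repeated-measures model for viral-load change use the Day 28 swab directly and would show catch-up.
- **Standing.** This is a secondary virology endpoint, and the SAP's multiplicity section covers only the interim analysis.

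Three stronger readings are tempting, and the documents do not support them. A reader might infer that the rule favours GT0918. It is the same in both arms, and its direction depends on which arm has more late first negatives. In the earlier trial placebo had not caught up (43.8% vs 10.0% still positive at Day 28). A reader might infer that the censoring date biases the hazard ratio. With no events after the Day 14 visit, censoring at Day 14 or Day 28 gives essentially the same log-rank test and Cox estimate. A reader might also infer that the two-negative rule should be dropped throughout. At Days 3, 7 and 14 a later swab is scheduled, so confirmation is possible there.

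None of this answers the central point: no scheduled swab can confirm a first negative at Day 28, and the SAP scores it as not cleared.

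**Conclusion.** The concern holds for the Day 28 clearance proportion and for any Day 28 reading of the time-to-clearance curve. The definition and the swab schedule alone establish it; no assumed rate is needed. The statement that Day 28 responders are the Day 14 responders requires complete swabs and no return to positive. The absence of curve events after the Day 14 visit requires that no unscheduled or early-withdrawal swab supplies one.

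The 7.4-point excess is an illustration, not a forecast for this trial. The point is worth correcting because a stated secondary endpoint is mislabelled and the remedy is cheap. It does not threaten the primary endpoint or the Day 28 viral-load change analyses.

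**What to change.** In SAP 4.10.3:

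1. Keep the two-negative rule and call it confirmed clearance.
2. Add the proportion with a negative swab at each of Days 3, 7, 14 and 28, analysed with the same GEE model. Use it as the measure for Day 28.
3. Label the Day 28 confirmed result as clearance beginning by Day 14 and still negative at Day 28, with a note on missing-swab and rebound patterns. Do not call it clearance by Day 28.
4. State that time to confirmed clearance is observable only to the Day 14 visit, and do not present the Day 28 Kaplan-Meier estimate as the proportion cleared by Day 28. No re-censoring is needed.
5. Check the same last-swab problem in two linked definitions. Sustained 100% viral reduction also needs two consecutive tests. Under viral resistance, a subject with no missing tests who is first negative at Day 28 counts as resistant.

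The cost is some SAP wording, extra table rows and one further model run on swabs already planned. The drawback is that a single negative at Day 28 may be false, which is why confirmed clearance should stay alongside it.
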